10.9. Appendix 9: Thrombotic Events to be Reported as Potential AESIs

At the time of protocol writing, the list of thrombotic events to be reported to the sponsor as potential AESIs is provided below. Further guidance may become available on thrombotic events of interest.

• MedDRA PTs for large vessel thrombosis and embolism

Aortic embolus, aortic thrombosis, aseptic cavernous sinus thrombosis, brain stem embolism, brain stem thrombosis, carotid arterial embolus, carotid artery thrombosis, cavernous sinus thrombosis, cerebral artery thrombosis, cerebral venous sinus thrombosis, cerebral venous thrombosis, superior sagittal sinus thrombosis, transverse sinus thrombosis, mesenteric artery embolism, mesenteric artery thrombosis, mesenteric vein thrombosis, splenic artery thrombosis, splenic embolism, splenic thrombosis, thrombosis mesenteric vessel, visceral venous thrombosis, hepatic artery embolism, hepatic artery thrombosis, hepatic vein embolism, hepatic vein thrombosis, portal vein embolism, portal vein thrombosis, portosplenomesenteric venous thrombosis, splenic vein thrombosis, spontaneous heparin-induced thrombocytopenia syndrome, femoral artery embolism, iliac artery embolism, jugular vein embolism, jugular vein thrombosis, subclavian artery embolism, subclavian vein thrombosis, obstetrical pulmonary embolism, pulmonary artery thrombosis, pulmonary thrombosis, pulmonary venous thrombosis, renal artery thrombosis, renal embolism, renal vein embolism, renal vein thrombosis, brachiocephalic vein thrombosis, vena cava embolism, vena cava thrombosis, truncus coeliacus thrombosis

• MedDRA PTs for more common thrombotic events

Axillary vein thrombosis, deep vein thrombosis, pulmonary embolism, MedDRA PTs for acute myocardial infarction*, MedDRA PTs for stroke*

Source: Shimabukuro T. CDC COVID-19 Vaccine Task Force. Thrombosis with thrombocytopenia syndrome (TTS) following Janssen COVID-19 vaccine. Advisory Committee on Immunization Practices (ACIP). April 23, 2021. https://www.cdc.gov/vaccines/acip/meetings/slides-2021-04-23.html.

*Vaccine Adverse Event Reporting System (VAERS) Standard Operating Procedures for COVID-19 (as of 29 January 2021) https://www.cdc.gov/vaccinesafety/pdf/VAERS-v2-SOP.pdf

10.10. Appendix 10: Guidance on Eligible Chronic Heart and Lung Conditions for Cohort 2

The following table presents a non-exhaustive list of chronic heart and lung conditions that are considered to either increase or not increase the risk for severe RSV infection. The list is intended to provide guidance to investigators to assess the eligibility of participants with existing chronic heart or lung conditions for participation in Cohort 2 of the study. Investigators must base their conclusion on the medical history, medication and patient interview as defined in Inclusion Criterion 10.

Conditions Considered to Increase the Risk	Conditions Considered not to Increase the
for Severe RSV Infection	Risk for Severe RSV Infection
Congestive heart failure	Hypertension
Coronary artery disease	Myxoma
 Angina pectoris 	Deviated septum
 Ischemic cardiomyopathy 	Pacemaker implantation
 Coronary arterial stent insertion 	Chronic cough
 Coronary artery bypass 	Aortic aneurism
Ischemic heart disease	Atrial fibrillation
Myocardial infarction	Carotid stent placement
Congenital heart disease (eg, Tetralogy of	Pulmonary embolism
Fallot)	COVID-19
Asthma (not including exercise induced)	Post COVID-19 syndrome
COPD	Cardiac arrhythmia
Interstitial lung disease	Sleep apnea
Sarcoidosis	Heart block
Idiopathic pulmonary fibrosis	Femoral artery stent placement
Stable asbestosis	Cardiac valve disease without chronic heart
Pulmonary hypertension	failure
1 difficility hypothesion	Carotid artery stenosis
	Left carotid stent placement
	Rhinosinusitis

10.11. Appendix 11: Protocol Amendment History

The Protocol Amendment Summary of Changes Table for the current amendment is located directly before the Table of Contents (TOC).

Amendment 1 (25 August 2021)

Overall Rationale for the Amendment: Following Health Authority feedback, the protocol is amended to revise the primary objective of the study by adding seroresponse rates in addition to neutralizing antibody GMTs as primary parameters to evaluate non-inferiority of immune responses in adults (including high-risk) relative to elderly (60 years and above). The primary immunogenicity endpoint is also modified from RSV preF IgG (by ELISA) to a functional immune marker (anti-RSV virus neutralizing antibodies). The statistical hypotheses and success criteria were revised accordingly, resulting also in a change in sample size and randomization ratios.

Section Number	Description of Change	Brief Rationale
and Name		
1.1 Synopsis 2.1 Study Rationale 3 OBJECTIVES AND ENDPOINTS 8.1 Immunogenicity Assessments 9.2.1 Immunogenicity 9.4.1 General Considerations 9.4.3.1 Primary Endpoints 9.4.3.2 Secondary/Exploratory Immunogenicity Endpoints	Sections throughout were updated to describe the revision of the immune endpoints and modification of assay.	Following Health Authority feedback.
1.1 Synopsis 3 OBJECTIVES AND ENDPOINTS	Secondary endpoint 'to assess the persistence of immune response post-vaccination' was changed into an exploratory endpoint	Antibody persistence at 6 months post-vaccination has been changed to an exploratory objective since this is the first study that assesses the durability of immune response in 18 to 59 year old individuals who are at risk for severe RSV disease.
1.1 Synopsis Table 1: Overview of the Cohorts, Groups, and Targeted Number of Participants 4.1 Overall Design 6.3 Measures to Minimize Bias: Randomization and Blinding 9.2 Sample Size Determination 9.2.1 Immunogenicity 9.2.2 Safety	Sections throughout were updated to describe the change in sample size and randomization ratios.	Following Health Authority feedback.

Section Number	Description of Change	Brief Rationale
and Name 1.1 Synopsis 1.3 Schedule of Activities 4.1 Overall Design 6.3 Measures to Minimize Bias: Randomization and Blinding 8 STUDY ASSESSMENTS AND PROCEDURES 8.1 Immunogenicity Assessments 9.2 Sample Size Determination	Blood will be collected from all participants to assess humoral immune responses.	Following Health Authority feedback.
2.2 Background 11 REFERENCES	Experience with Ad26-vectored vaccines was added.	For alignment with the other supportive Phase 3 study protocols.
1.1 Synopsis Table 1: Overview of the Cohorts, Groups, and Targeted Number of Participants	The following sentence was deleted: Recruitment will be optimized to target enrollment of at least 30% of participants in the 2 age categories, ie, 18 to 45 years and 46 to 59 years. Efforts will be made to have a comparable number of participants per region between the different cohorts.	No stratification is planned by region or by age category 18 to 45 and 46 to 59 years old. Monitoring of age and region distribution of enrolled participants per cohort will be part of the data surveillance during the study.
1.3 Schedule of Activities 10.3.3 Informed Consent Process	The following sentences were deleted: "Participants in the Immuno Subset and the Cellular Immuno Subset will need to consent for the additional blood collection in this subset." "Informed consent for additional blood collection will be requested from participants in the Immuno Subset and the Cellular Immuno Subset."	The informed consent for the additional blood collection for the Immuno Subset will be covered in a single overall informed consent form.
4.2.1 Study-Specific Ethical Design Considerations	The results of this study may be made available to all participants through a plain language summary at the conclusion of the study according to local standards/restrictions.	For alignment with the other supportive Phase 3 study protocols.
2.3.1 Risks Related to Study Participation 8.3.5 Pregnancy	In case of pregnancy, postnatal sequelae in the infant will no longer be followed-up.	According to the current Janssen SOP 'Receipt, Follow-up, and Reporting of Janssen Medicinal Product Individual Case Safety Reports', follow-up of postnatal sequelae in the infant is not a requirement. The sponsor protocol template is planned to be modified to reflect this change.

Section Number	Description of Change	Brief Rationale
and Name		
8.3.1 Time Period and Frequency for	The word 'symptomatic' was deleted	Definition of
Collecting AE, SAE, and AESI	from the definition of	thrombocytopenia is
Information	thrombocytopenia.	broadened to include all
8.3.6.1 Thrombosis with		cases of thrombocytopenia
Thrombocytopenia Syndrome		the investigators observe
		(including participant's
		routine blood test or blood
		test performed concomitantly
		to any AE/SAE/
		hospitalization, or any other)
		in the period of 6 months
		after vaccination; these
		should be reported as
		potential TTS cases (please
		refer to Section 8.3.6).
9.4.4 Safety Analyses	Subsection Physical Examinations was	For alignment with the other
	deleted.	supportive Phase 3 study
		protocols.
Throughout the protocol	Minor grammatical, formatting,	Minor errors were noted.
	spelling, and administrative changes	
	were made.	

#### AMENDMENT HISTORY

Table 1: SAP Version History Summary

SAP Version	Approval Date	Change	Rationale
1.0	21 September 2021	Not Applicable	Initial release
1.1	11 July 2022	Section 4, clarification of "as-treated" with respect to cohort assignment.	Non-substantial amendment prior to Database Lock.
		Section 5.3.2, specification of the weighting approach to use for the strata- adjusted difference in seroresponse.	
		Sections 5.1.2. and 5.4.1, Providing details on the AESI analysis	
		Appendix 2, mean and standard deviation were added for continuous baseline variables	

## 1. INTRODUCTION

This statistical analysis plan (SAP) contains information needed to perform the complete safety and immunogenicity analysis of the VAC18193RSV3006 trial. It applies to all the analyses described in Section 9.5 of the clinical trial protocol (CTP). The specifications of individual tables, listings and figures to be generated in each analysis will be described in a separate data presentation specifications (DPS) document.

## 1.1. Objectives and Endpoints

Refer to Section 3 of the CTP. The statistical hypotheses are described in Section 2 of this document.

# 1.2. Study Design

Refer to Section 4.1 of the CTP for more details on the study design, and Section 6.3 of the CTP for details on randomization and procedures for maintaining the blind.

#### 1.3. Planned analyses

Refer to Section 9.5 of the CTP for more details on the planned analyses.

# 2. STATISTICAL HYPOTHESES

To demonstrate the non-inferiority of the humoral immune response to Ad26/protein preF RSV vaccine in all adults aged 18 to 59 years (Group 1+3) versus in adults aged 65 years and older (Group 5) and in high-risk adults aged 18 to 59 years (Group 3) versus in adults aged 65 years and older (Group 5) in terms of neutralizing antibody GMTs and seroresponse rates.

The following hypotheses will be tested sequentially:

#### Null Hypothesis 1:

• Ad26/protein preF RSV vaccine induces inferior humoral immune response in terms of VNA A2 antibody GMTs at Day 15 in adults aged 18 to 59 years (Groups 1 and 3) versus in adults aged 65 years and older (Group 5).

OR

• Ad26/protein preF RSV vaccine induces inferior humoral immune response in terms of seroresponse rates of VNA A2 antibody titers at Day 15 in adults aged 18 to 59 years (Groups 1 and 3) versus in adults aged 65 years and older (Group 5).

#### Alternative Hypothesis 1:

• Ad26/protein preF RSV vaccine induces non-inferior humoral responses in terms of VNA A2 antibody GMTs at Day 15 in adults aged 18 to 59 years (Groups 1 and 3) versus in adults aged 65 years and older (Group 5).

AND

• Ad26/protein preF RSV vaccine induces non-inferior humoral responses in terms of seroresponse rates of VNA A2 antibody titers at Day 15 in adults aged 18 to 59 years (Groups 1 and 3) versus in adults aged 65 years and older (Group 5).

#### Success Criterion 1 (All Adults):

Non-inferiority of immune response in all adults is demonstrated:

 if the lower limit of the 2-sided 95% confidence interval (CI) for the VNA A2 GMT ratio of all adults aged 18 to 59 years versus in adults aged 65 years and older (GMTGroup 1+3/GMTGroup 5) is >0.67.

AND

• if the lower limit of the 2-sided 95% CI for the seroresponse rate difference of all adults aged 18 to 59 years versus in adults aged 65 years and older (Seroresponse Rate Group 1+3 – Seroresponse Rate Group 5) based on the VNA A2 antibody titers is >-10%a.

If non-inferiority is demonstrated in all adults for both neutralizing antibody GMTs and seroresponse rates, then the following hypothesis will be tested:

#### Null Hypothesis 2:

• Ad26/protein preF RSV vaccine induces inferior humoral response in terms of VNA A2 antibody GMTs at Day 15 in high-risk adults aged 18 to 59 years (Group 3) versus in adults aged 65 years and older (Group 5).

OR

• Ad26/protein preF RSV vaccine induces inferior humoral response in terms of seroresponse rates of VNA A2 antibody titers at Day 15 in high-risk adults aged 18 to 59 years (Group 3) versus in adults aged 65 years and older (Group 5).

#### Alternative Hypothesis 2:

• Ad26/protein preF RSV vaccine induces non-inferior humoral response in terms of VNA A2 antibody GMTs at Day 15 in high-risk adults aged 18 to 59 years (Group 3) versus in adults aged 65 years and older (Group 5)

AND

• Ad26/protein preF RSV vaccine induces non-inferior humoral response in terms of seroresponse rates of VNA A2 antibody titers at Day 15 in high-risk adults aged 18 to 59 years (Groups 3) versus in adults aged 65 years and older (Group 5).

#### Success Criterion 2 (High-risk Adults):

Non-inferiority of immune response in high-risk adults is demonstrated:

• if the lower limit of the 2-sided 95% CI for the VNA A2 GMT ratio of high-risk adults aged 18 to 59 years versus in adults aged 65 years and older (GMTGroup 3/GMTGroup 5) is >0.67.

<sup>a Note that the boundary of -0.1 on the proportion scale is equivalent to -10% on the percentage scale.

#### AND

• if the lower limit of the 2-sided 95% CI for the seroresponse rate difference of high-risk adults aged 18 to 59 years versus in adults aged 65 years and older (Seroresponse Rate Group 3 – Seroresponse Rate Group 5) based on the VNA A2 antibody titers is >-10%a.

### 3. SAMPLE SIZE DETERMINATION

Refer to Section 9.2 of the CTP.

# 4. POPULATIONS (ANALYSIS SETS) FOR ANALYSIS

For vaccine studies, study intervention assignment and, for this study, cohort assignment, will follow the as treated principle. Study participants will be analyzed according to the actual vaccine regimen received and their actual age and risk level (versus what they have been assigned at randomization).

Analysis Sets	Description
All Screened	This analysis set includes all participants screened for
	the study, regardless if they were screen failures or they
	got enrolled in the study.
	Rescreened participants are counted only once.
Full Analysis Set (FAS)	The full analysis set (FAS) will include all participants
	who received at least 1 study vaccination, regardless of
	the occurrence of protocol deviations and vaccine type
	(study vaccine or placebo).
	All safety and participant information analyses will be
	based on the FAS.
Per Protocol Immunogenicity Analysis Set (PPI)	The Per Protocol Immunogenicity Analysis Set will
	include all randomized participants who received study
	vaccine and for whom immunogenicity data are
	available. Samples taken after a participant experiences a
	impunganisity outcomes will be excluded from the DD
	analysis
	The list of major protocol deviations that would lead to
	elimination from the immunogenicity analysis will be
	specified in the major protocol violation criteria
	document, which will be finalized before database lock
	and unblinding.
	-8.
	The primary analysis set for analyses related to RSV
	immunogenicity is the PPI Set. As a sensitivity analysis,
	key tables may also be based on the FA Set.

#### Table 2: Analysis Sets

<sup>a Note that the boundary of -0.1 on the proportion scale is equivalent to -10% on the percentage scale.

# 5. STATISTICAL ANALYSES

### 5.1. General Considerations

### 5.1.1. Study Phases

A baseline (or reference) value will be defined as the value of the last available assessment prior to vaccination on Day 1. If there was no immunogenicity assessment done pre-vaccination, the assessment post-vaccination on Day 1 can be used as the baseline value for the immunogenicity analysis, if available.

The results of the safety analysis will be presented by phase. Immunogenicity results will be presented per scheduled time point as appropriate. Listings will be shown per phase and time point.

Study day or relative day is defined as follows:

- Study Day = visit date date of Day 1 + 1; if visit date ≥ date of Day 1 (date of first vaccination).
- Study Day = visit date date of Day 1; if visit date < date of Day 1 (date of first vaccination).

### 5.1.2. Phase Definitions

The phases in the study will be constructed as follows:

	Phase		Period	Interval			
Phase	#	Period	#	From	То		
Screening	1			Date and time of signing	One minute prior to start of post dose 1		
D .	2	D	1		period		
Regimen	2	Post-	1	Date and time of first	Minimum of:		
		dose		vaccination	a) 23:59 at the date of last contact		
					(for early discontinuation)		
					b) 23:59 at the database cut-off date		
					for analyses conducted before the		
					final analysis.		
					c) maximum of (28 days after		
					vaccination at 23:59, scheduled		
					visit 28 days after vaccination at		
					23:59)		
Follow-	3			One minute after Post-dose	Minimum of:		
up				period end	a) 23:59 at the date of last contact		
-				-	(for early discontinuation or		
					participants that completed the		
					study)		
					b) 23:59 at the database cut-off date		
					for analyses conducted before the		
					final analysis		

#### Table 3: Phase Definitions

The adverse events of special interest (AESI) analysis will be performed once by phase and once by time interval. The definition of the time intervals is shown in the table below. Additionally, in the tables a '0-56 days post-dose' interval and a '0-6 months post-dose' interval should also be

shown. The '0-56 days post-dose' interval is the combination of the '0 - 28 days post-dose' interval and the '29 - 56 days post-dose' interval. The '0-6 months post-dose' interval is the combination of the '0 - 28 days post-dose', '29 - 56 days post-dose' and '57 days - 6 months post-dose' intervals.

Dose	Interval	From	to
Post-vaccination	0 - 28 days post dose	Date time of the 1 st vaccination	
 
Min of:
 
23:59 at date of last contact (for discontinuations)
 
23:59 at date of DB cut-off for interim analyses
 
Maximum (Date of Vaccination 1 + 28 days at 23:59, date of scheduled visit 4 weeks after 1st vaccination at 23:59)
 

	29 - 56 days post dose	One minute after the end of the interval 0- 28 days post dose	
 
Min of:
 
23:59 at date of last contact (for discontinuations)
 
23:59 at date of DB cut-off for interim analyses
 
Date of Vaccination 1 + 56 days at 23:59
 

	57 days - 6 months post-dose	One minute after the end of the interval 29 - 56 days post dose	
 
Min of:
 
23:59 at date of last contact (for discontinuations/completions)
 
23:59 at date of DB cut-off for interim analyses
 

Table 4:	Definition	of intervals

# 5.1.3. Immunogenicity Visit Windows

For the immunogenicity analysis, assessments will be allocated to an analysis visit based on the planned visit as captured in the CRF. Visits that are out of the protocol-defined visit windows (see table below) will not be included in the per-protocol immunogenicity analysis. However, they may be included in sensitivity analyses.

 Table 5: Immunogenicity timepoints

Analysis timepoint	Reference day	Target day (counted from the reference day)	Window
Baseline	Day of vaccination 1	1	(-inf, 1]
Day 15	Day of vaccination 1	15	[12, 18]
Day 183	Day of vaccination 1	183	[169, 197]

#### 5.2. Participant Dispositions

Participant information will be shown for the full analysis set.

The number of participants in the following disposition categories will be summarized throughout the study by intervention group and overall:

- participants screened
- participants in the FAS
- participants vaccinated and not randomized
- participants randomized and not vaccinated
- participants not randomized and not vaccinated
- participants randomized and vaccinated
- participants who discontinued study
- reasons for termination

Also, the number of participants and percentage per phase will be tabulated.

Other participant information variables: demographics and baseline characteristics, major protocol deviations, and concomitant medications will be analyzed as described in Appendix 2, Appendix 3 and Appendix 4, respectively. Medical history and concomitant diseases will be tabulated.

# 5.3. Primary Immunogenicity Endpoint Analysis

# 5.3.1. Definition of Endpoint

The primary immunogenicity endpoints are:

- Neutralizing antibody titers against RSV A2 strain at 14 days after vaccination
- Seroresponse rate\* at 14 days after vaccination as determined by neutralization assay (VNA-A2)
- \* Seroresponse is defined as a 4-fold increase from baseline in Day 15 VNA A2 antibody titers.

The statistical hypotheses are described in Section 2.

# 5.3.2. Analysis Methods

The primary immunogenicity objectives will be assessed sequentially.

To assess non-inferiority in terms of GMTs, 2-sided CIs will be calculated for the difference in log2-transformed VNA A2 antibody titers at 14 days after active vaccination between all adults aged 18 to 59 years (Groups 1 and 3) and adults aged 65 years and older (Group 5) and between high-risk adults aged 18 to 59 years (Group 3) and adults aged 65 years and older (Group 5). The GMT ratio and CIs for the neutralizing antibody GMT objectives will be calculated via an analysis of variance (ANOVA) including both active groups (ie, Groups 1, 3, and 5) with Day 15 (ie, 14 days after vaccination) VNA A2 antibody titers as dependent variable and group as independent variable and COVID-19 vaccination as a stratification factor (3 categories: 1. Janssen COVID-19 vaccine, 2. Vaxzevria (Oxford/AstraZeneca), 3. other vaccine, or no vaccine). The CIs around the

difference will be back-transformed (by exponentiation) to CIs around a GMT ratio  $(GMT_{Group x}/GMT_{Group 5}, with x=1+3 \text{ or } x=3)$  and compared to the non-inferiority limit of 0.67 (2/3).

To assess non-inferiority in terms of seroresponse rates (co-primary objective), 2-sided CIs will be calculated for the difference in seroresponse rates 14 days after active vaccination for the same comparisons. Seroresponse based on VNA A2 antibody titers is defined as a 4-fold increase from baseline on Day 15. The Newcombe (Score) with continuity correction method will be used to calculate the CIs for the difference in seroresponse rates (Seroresponse Rate  $_{Group x}$  – Seroresponse Rate  $_{Group 5}$ , with x=1+3 or x=3) in percentage and compared with the non-inferiority margin of -10%. This analysis will be stratified for COVID-19 vaccination, applying Cochran-Mantel-Haenszel weightings to yield a strata-adjusted difference in seroresponse.

Non-inferiority of the humoral immune response to Ad26/protein preF RSV vaccine in all adults aged 18 to 59 years (Groups 1 and 3) versus in adults aged 65 years and older (Group 5) is demonstrated if the lower limit of the 2-sided 95% CI of the estimated GMT ratio is >0.67 and if the lower limit of the 2-sided 95% CI of the estimated difference in seroresponse rate is >-10%.

If non-inferiority in all adults aged 18 to 59 years (Groups 1 and 3) is not demonstrated for both neutralizing antibody GMTs and seroresponse rates, the study fails. If non-inferiority in all adults aged 18 to 59 years is demonstrated for both neutralizing antibody GMTs and seroresponse rates, then non-inferiority in high-risk adults aged 18 to 59 years (Group 3) can be tested, similarly as the comparison between all adults aged 18 to 59 years (Groups 1 and 3) and adults aged 65 years and older (Group 5), stratified for COVID-19 vaccination. Non-inferiority of the humoral immune response to Ad26/protein preF RSV vaccine in high-risk adults aged 18 to 59 years (Group 3) versus in adults aged 65 years and older (Group 5) is demonstrated if the lower limit of the 2-sided 95% CI of the estimated GMT ratio is >0.67 and if the lower limit of the 2-sided 95% CI of the estimated difference in seroresponse rate is >-10%.

As a sensitivity analysis to assess the impact of baseline titers, the neutralizing antibody GMT primary endpoint will also be evaluated adjusting for the respective baseline titers. For immunogenicity, baseline is considered as the last assessment pre-vaccination. In a second sensitivity analysis, different variances between the groups will be allowed. Therefore, the CIs will be calculated via Welch's ANOVA.

The significance level ( $\alpha$ ) is 5% (2-sided). No multiplicity adjustments are needed since the cohorts are tested sequentially in the overall 18 to 59 years group (Groups 1 and 3) followed by the high risk 18 to 59 years group (Group 3) and since non-inferiority based on GMTs and seroresponse rate both need to be met for each comparison, and as no interim analyses are planned before the primary analysis.

The population for analyses related RSV immunogenicity is the PPI set. The choice of population for the different analyses are described in Section 4.

CONFIDENTIAL – FOIA Exemptions Apply in U.S.

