9.2. Sample Size Determination

9.2.1. Immunogenicity

Immunogenicity assessments will be performed in all participants (N 1,113).

Sample size calculations for the immunogenicity objectives are performed under the following assumptions.

For the humoral immune response in terms of neutralizing antibody GMTs:

• no difference between high-risk adults aged 18 to 59 years and adults aged 65 years and older and no difference between high-risk adults aged 18 to 59 years and adults aged 65 years and older (ie, assuming a true GMT ratio of Day 15 [ie, 14 days after vaccination] RSV A2 neutralizing antibody titers equal to 1 for those comparisons, and similar standard deviation)

- a standard deviation of 1.5 at the log₂ scale for VNA A2 on Day 15^a
- non-inferiority limit of 0.67 (2/3)
- 1-sided α of 2.5%

For the humoral immune response in terms of neutralizing antibody seroresponse rates (defined as a 4-fold increase from baseline in Day 15 antibody titers):

- Seroresponse rates are assumed to be 85% in all adults aged 18 to 59 years, high risk adults aged 18 to 59 years and adults aged 65 years and older, based on available data from Phase 1/2 clinical studies,
- Non-inferiority margin of 10%
- 1-sided α of 2.5%

In addition:

- a ratio of 1:1:1 for the active groups in Cohorts 1, 2, and 3
- hierarchical testing (ie, test first Group 1+3 versus Group 5, if non-inferiority is demonstrated: test Group 3 versus Group 5)

Simulations show that a total of 285 evaluable participants per active group in each cohort are needed to have 90% power to demonstrate non-inferiority in terms of neutralizing antibody GMT and seroresponse rates between high-risk adults aged 18 to 59 years and adults aged 65 years and older. With this sample size, the power to demonstrate non-inferiority in terms of neutralizing antibody GMT and seroresponse rates between all adults aged 18 to 59 years and adults aged 65 years and older is >95%. The power to demonstrate non-inferiority for the high-risk adults aged 18 to 59 years and adults aged 65 years and older is approximately 90%, taking into account the testing strategy (sequential testing). To account for exclusions from the Per-protocol Immunogenicity Set (see Section 9.3), drop-outs, and missing samples, approximately 315 participants per active group should be enrolled.

9.2.2. **Safety**

Solicited AEs, unsolicited AEs SAEs, and AESIs will be collected in all participants (N 1,113).

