9.4. Statistical Analyses

The SAP will be finalized prior to database lock of the primary analysis and it will include a more technical and detailed description of the statistical analyses described in this section. This section is a summary of the planned statistical analyses of all endpoints.

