9.4.3. Immunogenicity Analyses

9.4.3.1. Primary Endpoints

The primary immunogenicity objectives will be assessed sequentially.

To assess non-inferiority in terms of GMTs, 2-sided CIs will be calculated for the difference in log₂-transformed VNA A2 antibody titers at 14 days after active vaccination between all adults aged 18 to 59 years (Groups 1 and 3) and adults aged 65 years and older (Group 5) and between high-risk adults aged 18 to 59 years (Group 3) and adults aged 65 years and older (Group 5). The GMT ratio and CIs for the neutralizing antibody GMT objectives will be calculated via an analysis of variance (ANOVA) including both active groups (ie, Groups 1, 3, and 5) with Day 15 (ie, 14 days after vaccination) VNA A2 antibody titers as dependent variable and group as independent variable and COVID-19 vaccination as a stratification factor (3 categories: 1. Janssen COVID-19 vaccine, 2. Vaxzevria (Oxford/AstraZeneca), 3. other vaccine, or no vaccine). The CIs around the difference will be back-transformed (by exponentiation) to CIs around a GMT ratio

 $(GMT_{Group x}/GMT_{Group 5}, with x 1+3 or x 3)$ and compared to the non-inferiority limit of 0.67 (2/3).

To assess non-inferiority in terms of seroresponse rates (co-primary objective), 2-sided CIs will be calculated for the difference in seroresponse rates 14 days after active vaccination for the same comparisons. Seroresponse based on VNA A2 antibody titers is defined as a 4-fold increase from baseline on Day 15. The Newcombe (Score) with continuity correction method will be used to calculate the CIs for the difference in seroresponse rates (Seroresponse Rate Group x Seroresponse Rate Group 5, with x 1+3 or x 3) and compared with the non-inferiority margin of -0.1. This analysis will be stratified for COVID-19 vaccination.

Non-inferiority of the humoral immune response to Ad26/protein preF RSV vaccine in all adults aged 18 to 59 years (Groups 1 and 3) versus in adults aged 65 years and older (Group 5) is demonstrated if the lower limit of the 2-sided 95% CI of the estimated GMT ratio is >0.67 and if the lower limit of the 2-sided 95% CI of the estimated difference in seroresponse rates is >-0.1.

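### Does SAP 5.3.2 need to spell out how the Newcombe interval and the CMH weights combine for the seroresponse difference?

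*SAP*

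**What the plan says.** Protocol 9.4.3.1 names the interval and says only: "This analysis will be stratified for COVID-19 vaccination". SAP 5.3.2 keeps the interval ("The Newcombe (Score) with continuity correction method will be used to calculate the CIs for the difference in seroresponse rates") and adds the weights: "This analysis will be stratified for COVID-19 vaccination, applying Cochran-Mantel-Haenszel weightings to yield a strata-adjusted difference in seroresponse". The Amendment History of the SAP describes the version 1.1 change to this section as "specification of the weighting approach to use" for the adjusted difference. Success requires the lower 95% limit to exceed -10%, first for Groups 1+3 versus Group 5 and then for Group 3 versus Group 5.

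On where such detail belongs, Protocol 9.4 says of the SAP that "it will include a more technical and detailed description of the statistical analyses described in this section". SAP 1 states: "This statistical analysis plan (SAP) contains information needed to perform the complete safety and immunogenicity analysis of the VAC18193RSV3006 trial". It leaves to a separate data presentation specifications document "The specifications of individual tables, listings and figures to be generated in each analysis". SAP 5.5.1.2.2 also sends some calculation detail (for ICS values) to that document, which is not among those available here.

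**The concern.** Newcombe's interval is defined for two simple proportions, while CMH weights define a weighted difference over strata. Joining them takes choices that the SAP does not make: one pair of score limits on weighted rates or a pair per stratum, which sample size enters, and whether the correction is applied once or three times.

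This interval decides a co-primary criterion. If the all-adults comparison fails, the study fails; if the high-risk comparison fails, the high-risk claim is lost. One data set should give one answer. Here two analysts following the same text could land on opposite sides of -10%, and the SAP says that it holds what is needed for the complete analysis.

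**Working it through.** **Inputs.** From Protocol 9.2.1: 285 evaluable per active group, seroresponse 85% in every group, margin 10 points, "1-sided α of 2.5" per cent, SD 1.5 on the log2 scale, GMT limit 0.67, true GMT ratio 1. Assumed, because the documents do not give them: stratum shares of 33/33/33, 10/10/80 and 5/5/90, the same in both groups, plus one unequal case.

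**The plan's own power, unstratified.**
- GMT, Group 3 v 5: SE = 1.5·√(2/285) = 0.1257. -log2(0.67)/SE = 0.5778/0.1257 = 4.598. Power = Φ(4.598 - 1.960) = 99.6%.
- Seroresponse, exact enumeration of the corrected Newcombe interval: 90.2%. One-sided error at 75% v 85%: 2.17%.
- Joint, taking the endpoints as independent: 0.996 × 0.902 = 89.8%. With sequential testing, simulation gives 89.6%. All adults (570 v 285): 97.9%.

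These agree with the stated 90% and >95%.

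**Boundary example.** Group 3 has 78, 77 and 78 of 95 (233/285 = 0.8175). Group 5 has 81, 81 and 81 of 95 (243/285 = 0.8526). The difference is -0.0351, each CMH weight is W = 1/3, and z = 1.960. The corrected Wilson lower limit is

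L = {2np + z² - 1 - z√[z² - 2 - 1/n + 4p(n(1-p) + 1)]} / {2(n + z²)},

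and the upper limit U mirrors it.

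1. *One correction, on weighted rates with n_eff = 1/Σ(W²/n) = 285.* L for Group 3 = 0.7667; U for Group 5 = 0.8906. Lower limit = -0.0351 - √(0.0509² + 0.0380²) = **-0.0986**.
2. *Corrected Newcombe distances per stratum, squared and summed with W².* The Group 3 distances are 0.0949, 0.0961 and 0.0949; each Group 5 distance is 0.0616. Lower limit = -0.0351 - √(0.03864/9) = **-0.1006**.
3. *Corrected Wilson limits per stratum with relaxed z = 1.960/√3 = 1.132, then weighted.* L = 0.7629; U = 0.8937. Lower limit = -0.0351 - √(0.0546² + 0.0410²) = **-0.1034**.
4. *Limits as in 3, with the variance evaluated at those limits.* Lower limit = -0.0351 - 1.960·√[(0.1809 + 0.0950)/285] = **-0.0961**.

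Forms 1 and 4 pass; 2 and 3 fail. Forms 2, 3 and 4 all correct in every stratum, so placing the correction there does not by itself make the interval stricter.

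**Operating characteristics** (200,000 simulated trials per mix, equal mixes in both groups):

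| Form | Seroresponse power | One-sided error at 75% v 85% |
|---|---|---|
| 1 | 90.0–90.1% | 2.1–2.2% |
| 2 | 88.8–89.6% | 1.9–2.1% |
| 3 | 86.3–87.1% | 1.5–1.6% |
| 4 | 91.2–91.5% | about 2.5–2.7% |

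Subtracting one correction term, ½(1/n1 + 1/n2), from the uncorrected stratified limit gives power of 89.2–89.4% and error of 2.0–2.1%.

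**Size at the margin.** With Group 5 at 242/285 and near-equal strata, Group 3 needs 232 responders under form 1, 233 under form 2 and 234 under form 3. One responder is 1/285 = 0.35 points. Form 1 passes while form 2 fails in 0.6–1.3% of trials; form 1 passes while form 3 fails in 3.0–3.8%. For 570 v 285, constructions in a separate comparison differed by 0–1 responder with equal or mildly unequal mixes.

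**Unequal mixes.** Take strata of 28/14/243 v 14/86/185. The CMH weights n1·n2/(n1+n2) are 9.33, 12.04 and 105.04, so W = 0.074, 0.095 and 0.831. Then n_eff = 1/Σ(W²/n) is about 271 for Group 3 and 237 for Group 5. Power is about 87% under form 1 and runs from about 82% to 89% over all forms tried. At 570 v 285 the gap becomes 2–3 responders.

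**The case for a change.** The best case for a change is that it costs one sentence, that the SAP is the right home for it, and that version 1.1 reopened this very section and stopped one step short. The text does not even fix the ordering of strict and lenient: forms 3 and 4 both start from stratified Wilson limits, yet one is the strictest and the other the most lenient in the table. Nor are all readings conservative, since form 4 reaches about 2.7%. Groups 3 and 5 come from different cohorts, and Protocol 6.3 randomizes active against placebo within a cohort, so equal vaccine mixes are not assured.

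Most of this stands as description. The documents available do not give the formula, and writing it down would be good practice. It does not show that following the plan gives a wrong result. With equal mixes, an analyst who always took the most lenient form tested would exceed the nominal 2.5% by about 0.2 points at most; the strictest form costs about 4 points of power. Under unequal mixes, part of the power loss comes from the smaller effective sample sizes, and naming a formula would not recover that part. A stratum that is empty in one group gets CMH weight zero, so the stated weights already deal with that case.

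**Conclusion.** No change to the plan follows. The SAP fixes the interval family, the correction, the strata, the weights, the margin and the decision rule. What remains is a choice among constructions that a trial statistician would make sensibly. A single correction on the CMH-weighted rates is a natural reading, and it reproduces the planned power under equal mixes.

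The choice is worth 1 or 2 responders of 285 in almost every equal-mix case for Group 3 v 5, and usually 0 or 1 for the pooled comparison. It can alter the outcome only within about half a percentage point of -10%. Error stays near or below 2.5% (about 1.5–2.7%).

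This rests on assumed stratum shares, on the plan's 85% response rates and on the constructions tried. Strong imbalance between cohorts lowers power to about 82–89% and widens the pooled gap to 2–3 responders. A plain weighted average of per-stratum limits was left out as too conservative to be a reasonable reading. The point concerns reproducibility of documentation; no stated rule or figure is in error.
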